1.0 Objectives

1.1 Purpose:

The goal of this project is to examine the neural systems underlying the physiological responses to threat in children and adolescents, and to examine the effectiveness of various social partners (parent, friend) in buffering youth from the physiological and brain effects of threat.

2.0 Background

2.1 Significance of Research Question/Purpose & Existing Literature:

Social buffering, a key concept in the psychobiology of stress, describes a phenomenon in which the presence and availability of social partners reduces activity of threat- and stress-mediating neurobiological and neuroendocrine systems (Gunnar, 2017). It is a key pathway through which social support reduces stress (Uchino et al., 2012) and enhances health (Kaplan et al., 1977). Impaired social buffering is a primary pathway through which adverse childhood experiences get under the skin to affect development (Hostinar et al., 2014). Despite its centrality to stress or threat regulation, we know relatively little about the normative development of social buffering beyond the infant years.

2.2 Preliminary Data:

Prior behavioral data from our laboratories demonstrates that parents remain effective social buffers beyond infancy and throughout childhood. Among 9- and 10-year-olds, preparing for the Trier Social Stress Test (TSST) with a parent completely blocked elevations in cortisol to this social evaluative stressor (Hostinar et al., 2015). However, our results suggest that puberty results in a waning of parental HPA stress buffering effectiveness. Preparing for the TSST with the parent vs experimenter had no effect on 15- and 16-year-olds or on 11- to 14-year-olds who were at more advanced pubertal stages (Doom et al., 2016).

Supportive friendships are associated with many positive outcomes for children, while their lack is associated with negative emotionality (Laursen & Hartl, 2013). However, counter to our initial expectations, our results showed that preparing for the TSST with a friend *increased* rather than reduced the cortisol response for adolescents (Doom et al., 2015). Having the friend “help” may actually have amplified effects of social evaluation.

2.3 Study Aims:

The current study examines the neural response, as well as the physiological responses to threat-related stress across the transition to puberty. We use two standard threat learning paradigms that have been

used previously with adolescents. In this project, we will randomly assign youth to complete this testing under one of three social buffering conditions: presence of a parent, presence of a close friend, or no social support present (standard imaging condition).

The **long-term goal** of our research is to enrich understanding of threat-related stress regulation and its role in human development. The **overall objective** of this project is to understand normative processes in threat-related stress regulation and their neurobiological correlates as children leave childhood and become more autonomous in adolescence. The **central hypothesis** of this project is that early adolescence is a period of time when parental buffering wanes in efficacy, leaving many youth experiencing a relative dearth of relationships that can provide powerful stress buffers.

The aim of the current study is to delineate changes in brain activation in response to social buffering by parents and friends over the pubertal transition.

Hypothesis #1: Parental social buffering will result in increased activation in brain regions associated with safety (e.g. vmPFC) and lower activation in brain regions involved in fear and pain (e.g., insula, amygdala, hypothalamus), as well as tighter coupling between the vmPFC and amygdala activity, but these relationships will wane with pubertal development.

Hypothesis #2: Friend social buffering will result in less attenuation in the same brain regions, and less mPFC-Amygdala coupling than parental buffering, but will also become less effective with pubertal development.

Hypothesis #3: Neural activity associated with social buffering will mediate the effectiveness of physiological buffering by social partners.

3.0 Study Endpoints/Events/Outcomes

3.1 Primary Endpoint/Event/Outcome:

Neural activity in vmPFC, insula, amygdala, and hypothalamus; salivary cortisol, heart rate, respiration, skin conductance

3.2 Secondary Endpoint(s)/Event(s)/Outcome(s):

Exploration of possible sex differences in across buffering conditions later in puberty but not earlier in puberty.

4.0 Study Intervention(s)/Investigational Agent(s)

4.1 Description: Note that there are no investigational agent(s) (e.g., drug, device) being evaluated. The study qualifies as an intervention due to

random assignment into social buffering condition, to determine the effect of social partner on threat-related stress responses.

Child participants (10- to 15-year-olds) will be randomly assigned to one of three conditions during an fMRI version of a threat learning paradigm: (1) no social buffer, (2) presence of a parent, or (3) presence of a same-sex/similar-age close friend.

4.2 Drug/Device Handling: N/A

4.3 Biosafety: N/A

4.4 Stem Cells: N/A

5.0 Procedures Involved

5.1 Study Design: The study design is cross-sectional. 150 target children (10- to 15-year-olds) will be randomly assigned to one of three conditions: (1) no social support (standard MRI scanning condition); (2) presence of a parent; or (3) presence of a close friend. Outcome measures will be compared across the three social buffering conditions. Pubertal stage will be included as a continuous variable in analyses of physiological and/or brain responses.

Two tasks will be used during the MRI scanning. Both have been shown to activate stress-related regions of the brain in past studies and have been used by our labs. The order of these two tasks will be counterbalanced.

Based on the results of piloting social buffering will EITHER be done with the presence of a buffer in person, or, displayed on screen via a live Zoom feed. All conditions will use the same modality.

Study Overview:

Visit 1: Parent and child will participate in an online video session (via Zoom) lasting approximately 2 hours. Following a detailed overview of study and consent/assent procedures, participants will be asked to complete the following measures:

Parent:

- Questionnaire regarding family income, education level, and family composition
- Parent-report questionnaire about child's general health, behavior, and development (MacArthur Health Behavior Questionnaire; HBQ)
- Parent-report MRI safety screening questionnaire about the child to rule out any contraindications for MRI scanning
- *[If the child is randomized to the parent-present buffering condition],* self-report MRI safety screening questionnaire to rule out any contraindications for sitting in the MRI area

PROTOCOL TITLE: An MRI Study of Learning and Social Support

VERSION DATE: v.10 2024.12.18

- Child life challenges question

Children/adolescents:

- Questionnaire about general health, behavior, and development (MacArthur Health Behavior Questionnaire; HBQ)
- Questionnaire about their relationships with their parents and their best friend (Network of Relationships Questionnaire)
- Questionnaire about anxiety in different contexts (State-Trait Anxiety Inventory for Children)
- Pubertal development questionnaire (Morris and Udry, 1980)
- Safety screening questionnaire to confirm safety in the MRI scanner
- Perceived stress questionnaire
- Child life challenges questionnaire

Visit 2: Parent and child [*and sometimes, child's close friend*] will come to the Center for Magnetic Resonance Research for a session lasting approximately 2 hours. Note that if buffering occurs in person, we will invite the close friend to attend in person, and if buffering occurs on-line, we will invite them to attend via zoom. Following a session overview and consent/assent procedures, participants will be asked to complete the following measures:

Parent:

- Required safety screening questionnaire to confirm child's safety in the MRI scanner
- [*If the child is randomized to the parent-present buffering condition*], self-report MRI safety screening questionnaire to rule out any contraindications for sitting in the MRI area
- [*If the child is randomized to the parent-present buffering condition*], sit next to scanner bed and listen to music, radio, audio book, podcast, etc. or read a book for duration of MRI scan (approx. 1 hour) OR sit in a separate room while connected via video conference call to research staff in the MRI console room for duration of MRI scan, chatting with the child periodically.

Child:

- Required safety screening questionnaire to confirm child's safety in the MRI scanner
- Saliva sampling at up to 10 time points throughout the testing session to assess levels of stress-sensitive compounds, including cortisol, alpha amylase.
- Children chew on an absorbent sponge for 1-2 minutes to acquire each saliva sample.

- Practice in a pretend MRI machine to gain familiarity with the scanning environment and assess comfort in the scanner bore (i.e., rule out claustrophobia)
- Standard non-invasive structural and functional MRI scanning for 1 hour at 3-Tesla (clinical standard) field strength.
- Collection of physiological data during the MRI scan (respiration belt, pulse oximeter and/or 3 EKG leads, MRI-safe skin conductance electrodes on the fingers or palm of one hand or foot).
- Performance of two tasks during MRI scanning: one emotional faces matching task and one emotionally charged go-no go task.
- Completion of a post-scan survey to assess perceived stress at various points throughout the session.
- Optional: Wearing of an actigraphy device on the wrist for several days to record activity and sleep patterns.

Child's Friend: [Applicable only if the child is randomized to the friend-present buffering condition]

- MRI safety screening questionnaire to rule out any contraindications for sitting in the MRI area
- Completion of the Network of Relationships questionnaire
- Sit next to scanner bed and listen to music, radio, audio book, podcast, etc. or read a book for duration of MRI scan (approx. 1 hour) OR join the session online via video conference call to research staff in the MRI console room for duration of MRI scan , chatting with the first child periodically.
- *Note: Friend's parent will complete a full consent procedure over the telephone or video conference call prior to the session and will return a signed consent and child safety-screening form via REDCap or by mail or with the participating family.*

5.2 Study Procedures:

Social Buffering Manipulations: Will include 3 between-subjects conditions and both sexes. Participants will be randomly assigned to No Social Partner, Parent, or Close Friend conditions. Definition of Close Friend. We will ask the parent to have the child select the close same-sex friend they want to have accompany them. The parent then has to contact that child's family and get their permission for us to contact them. We have successfully conducted studies in which the child brings their best friend.

Affective Paradigms: Aversive Learning Paradigms: Consent, assent, and questionnaires will occur during an online session (to reduce in-person requirements; minimize the impact of COVID on study feasibility.) At the session, after a reminder of procedures, youth will be separated from their parents. Youth will be taken to a private changing room to change into

hospital scrubs prior to moving to the MRI scanner. An MRI-safe respiration belt, pulse oximeter and EKG electrodes, and SCR electrodes will be positioned for physiological assessment and the child will be given ear plugs, a button response box for behavioral ratings, and an emergency call button. Youth will rest and/or watch a video during structural MRI sequences (6-10 minutes), then lie quietly with eyes open for a 5-10 minute scan with no video or audio material. The experimenter will then remind the child of the instructions for the affective task, and scanning will begin with the start of the task. (1) In the first task, one target face or shape is presented at the top of the screen and two option faces or shapes are presented at the bottom of the screen. One of the bottom faces shows the same emotion, or is the same shape, as the top face or shape and the participant is instructed to quickly identify which face or shape matches and select that option using the button box in their hand. The task includes five blocks of shape matching and four blocks of face matching, with each block containing six trials. Each trial presents the stimuli for 4.5 seconds and has an interstimulus interval of 0.5 seconds. At the end of the task, the child will be given a chance to move their bodies and rest their eyes before moving on to the second task. (2) In the second task, a target letter is presented in the center of the screen with a large image in the background. Participants are instructed to press a button on the button box if the letter is not an 'X' and refrain from pressing when they see the letter 'X.' The images presented behind the letters are sourced from the International Affective Picture System (IAPS) and are presented in blocks of positive, negative, neutral, negative, or scrambled (masked) images. The task includes two blocks of each affective category (positive, negative, neutral, and scrambled) in addition to two all-go blocks which present no 'X' and two rest blocks which present only a fixation cross. Each block contains six trials which present stimuli for 0.85 seconds with a variable interstimulus interval of 0.5-0.8 seconds. Following the second fMRI task, children will be removed from the scanner and will complete a stress questionnaire. Saliva samples will be collected every 10-20 minutes throughout the scanning session, including between scan segments, to assess dynamic changes in stress-related hormones. In the scanner, this involves moving the child partway out of the scanner bore and using a long collection sponge that hangs out of the mouth to avoid any possibility of choking since the child is lying supine. We have used this method successfully in a previous study collecting saliva in the scanner environment. Following the stress questionnaire, the child will change back into their own clothing and return to the lobby to complete additional questionnaires and wait for up to 30 min while being sampled for stress hormones every 10 min.

Pubertal Development: We will create a summary pubertal development index from parent & child report. A planned nurse exam was dropped due

to COVID and funding considerations. Parents & youth will complete the Morris and Udry (1980) pubertal development questionnaire, which allows placement in Tanner stages for hair, testicles, and breast development.

Questionnaires.

Demographic Questionnaire: Parents will complete information on pre-tax family income, education level of parent(s), composition of the household, and medications that the child regularly takes.

Daily Diary: The parent and the youth both will report the following for the child that day: the time of wake up, medication usage, illness/fever, physical activity, and caffeine consumption.

Relationship Quality: Youth and their friend (when assigned to friend buffer condition) will complete the Network of Relationships Inventory (NRI, Furman & Buhrmester, 2009) for parents and their close friend. This questionnaire is based on an integration of attachment and Sullivanian theory and assesses three systems that are expected to be key in close relationships: attachment, caregiving and affiliation. The scales are: companionship, seek safe haven, seek secure base, provide safe haven, provide secure base, conflict, antagonism and criticism. We will also include the full set of scales from the NRI,: Each scale consists of 3 items scored on a 5-point Likert scale. Psychometric qualities are high. Condition differences in quality of relationships will be examined and included as covariates if groups differ significantly. Otherwise, in follow-up analyses we will examine whether social buffering effects are stronger in relationships the child views as more supportive.

MacArthur Health and Behavior Questionnaire (HBQ) for 9-18 Year-Olds (Parent and Child, 2.1): This questionnaire was developed by Marilyn Essex based on the original HBQ for 4-8 year olds. We have used it many times. The scales we proposed to use here have high reliabilities (Cronbach alpha's > .8). We will use the peer scales (acceptance/rejection, bullied, relational victimization, asocial, behavioral inhibition) and broad-band symptoms scales (Internalizing, Externalizing). These measures will be examined for balance across groups and if differences by condition, pubertal stage, or sex are found, will be entered as covariates.

State-Trait Anxiety Index: A brief scale to assess current and general anxiety, which might be an important covariate.

Self-Report of Stress: As a manipulation check, participants will rate their arousal and emotional state at various points during Visit 2.

Morris and Udry Pubertal Development Questionnaire: The parent and youth will both report on hair, testes, and breast development.

Responses to Stress Questionnaire: Includes a checklist of stressors and how often they have occurred recently, then asks how respondents coped with each stressor listed and what coping methods were used more often.

Child Life Events Inventory: Parent reports on past significant events in the child's life that may have caused trauma, stress, or other relevant outcomes.

Sleep Diary: Child reports on daily sleep habits over several days including timing of falling asleep and waking, perceived sleep quality, and sleep disruptions. This sleep diary would be completed once a day for up to 14 days.

Perceived Stress Scale: Child reports on perceptions of life stress over the past month.

Child Life Challenges: Parent reports on their child's global lifetime adversity exposure.

Child Life Challenges: Child reports on their global lifetime adversity exposure.

Physiological Measures.

Stress Hormones: We will assay saliva samples for stress sensitive hormones: cortisol and alpha-amylase. Saliva will be collected using SalivaBio Oral Swabs (SOS) or passive drool and stored frozen at -20°C until shipped for assay. Medications will be recorded from parent report and classes of drug codes will be used to group meds by presumed mechanisms of action and will be entered as covariates (Granger et al., 2009). Systemic glucocorticoid medications are an exclusion criterion. For each analyte, we will calculate area under the curve from intercept (AUCi) to provide a single measure for the main analysis.

Hair Hormones: Hair will be assayed for a full panel of stress, puberty, and sleep hormones. Hair cortisol provides a measure of the stress sensitive hormone cortisol indexed over approximately 3 months. We will take the ~ 3 cm of hair next to the scalp on the posterior vertex. Based on an average hair growth rate of 1 cm/month, this represents hair grown over the 3-month period prior to sampling. Wash and steroid extraction procedures will be conducted in [name]'s ISO lab, following their published protocol (Stalder & [name], 2012, study II) with 7.5 mg of hair used for analysis. Participants will also complete a questionnaire about hair products and treatment that can be included as covariates. We anticipate that we will not be able to collect hair cortisol for some participants whose hair is too short or who refuse this sampling. In previous work, we have

had missing samples for ~ 10% of participants. We will deal with this using multiple imputation by chained equations (MICE) to impute missing data.

Physiological Recording: Participants will wear a combination of standard Siemens physiological recording equipment for the MRI environment (respiration belt, pulse oximeter, EKG leads). In addition, they will wear BioPac MRI-safe skin conductance electrodes. Samples will be collected throughout the entire MRI scan. Response measures will be computed by regressing aversive learning condition values on comparison values during the resting state scan and saving the residual as the response measure. If the parent and child opt-in, the child will wear an actigraphy device for several days. The actigraphy device uses accelerometers and gyroscopes to measure body movement. After completion of actigraphy data collection, the parent will return the device back to the researchers.

All questionnaires and surveys are included in the ETHOS portal. Contact information and child age will be obtained from an existing registry of families who have expressed interest in child development research (specifically, parent name(s), address, phone number, email address, child name, child sex, and child birthdate). All other data will be acquired directly from the participants, and information obtained from the participant registry will be verified verbally with the parent. Birthdate will be collected from parent at the session so that a precise age of child can be obtained.

5.3 Study Duration: Participants will participate in two sessions, one online, and the other in-person. Each session will last approximately 2 hours.

- All participants will be enrolled and assessed within approximately 42-months.
- Primary data analysis endpoints will be available within 6-12 months of the end of data collection (i.e., end of 5-year grant funding cycle).

5.4 Individually Identifiable Health Information: This study will collect health information directly from participants. A HIPCO survey has been uploaded in the ETHOS portal.

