15.0 Statistical Considerations

15.1 Data Analysis Plan:

Preliminary Analyses to Determine Covariates Needed for Primary Analyses.

The purpose of collecting data on potential covariates is to identify variables

that are correlated with both the independent variable (social buffering condition, sex, pubertal stage) and the primary outcome measures. Those covariates that are associated with the independent and outcome variables will be controlled for in the primary analyses. Those that are not will be used to describe the sample, but will not need to be included in the analyses to obtain unbiased estimates. For each potential covariate, we will conduct correlations or t-tests with pubertal stage, and t-tests, ANOVAs, or chi-square tests (as appropriate) with sex and condition. If data do not confirm to modeling assumptions, we will use nonparametric analogs instead.

Preliminary Analyses of Imaging Data to Yield Primary Outcome Measures: fMRI data will be analyzed in FSL software (version 6.0.1) to generate voxel-wise contrast maps. Mean signal values will be extracted from these maps in a priori regions of interest for every participant using the methods described below. These preliminary analyses are used to generate the fMRI outcome variables of interest. The values of these outcome variables for each participant will be used in the general statistical analyses described in the next section. In total, these preliminary analyses will yield 6 primary task-related outcome variables, and 6 primary connectivity-related outcome variables.

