15.2 Power Analysis: For the power analysis for the primary analyses, we calculated the minimum detectable effect size (MDES) assuming $n = 200$, a $\alpha = .05$, and power = .80 with 12 covariates in our model. Power was estimated in R (R Core Team) using the pwr library (Champely, 2018). A power analysis was performed to quantify the minimum detectable effect size (f^2) for a three-way interaction between social buffering condition, sex, and pubertal stage within a multiple regression model controlling for the 12 covariates, all two-way interactions, and the main effects (the most complex model considered in our primary analysis, see Equation 1 below). Assuming these conditions, we should be able to detect an f^2 of 0.056. In other words, adding the three-way interaction to a model containing the covariates and all lower order interactions and main effects, the three-way interaction would need to explain an additional 5.6% of the variability to be detected. This falls between Cohen's criteria for a small ($f^2 = .02$) and medium effect ($f^2 = .15$) (Cohen, 1988). With a sample size of 200, even if we lose 40 of the participants to movement artifact for the imaging analyses, assuming all the previous conditions but a sample size of 160, we will still have an f^2 of .070, or still within a small-medium effect size. As the number of covariates decreases, the size of the MDES will decrease. Therefore, this represents a conservative estimate of the power for our primary analyses as we are likely to have fewer covariates in our models

and will use multiple imputation to correct for missing data. For the two-way interaction and main effects models, described below, the power will be larger than these reported values as the models will be simpler.

15.3 Statistical Analysis of MRI and non-MRI Outcome Variables:

The following is a list of the analyses that we will perform on the outcome measures. They are classified as to whether they are the primary or mediational analyses. All statistical analyses will be performed in R.

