The primary analyses will consist of a series of multiple regression models. For each dependent variable, variation in neural activity, cortisol, and physiological responses, we will begin by testing the three-way interaction between social buffering condition, sex, and pubertal stage for all outcomes. If the three-way interaction is not significant, we will then examine all two-way interactions. If the two-way interactions are not significant, we will then examine main effects only models. If the three-way interaction is significant, we will not examine any other model. If condition is significant as an interaction or as a main effect, we will examine all pairwise comparisons using Tukey's Honestly Significant Difference test.

Multiplicity of testing. We will correct for multiple comparisons using the Benjamini-Hochberg (BH) correction. The BH method works by controlling the false discovery rate, and relative to the Bonferroni's correction is more powerful, while still adequately protecting against Type I error (Williams, Jones, & Tukey, 1999).

Mediational Analysis. When changes in activity of brain regions differ by condition or condition by pubertal status and we also see condition or condition by pubertal status differences for cortisol or physiological measures, then we will examine whether brain activity differences mediate the neuroendocrine or physiological differences. This will be examined using path analysis, while controlling for covariates identified in the preliminary covariate analysis, and will be estimated using the lavaan package in R (Rosseel, 2012).

The significance of all indirect effects will be assessed using bias-corrected 95% confidence intervals (Efron & Tibshirani, 1986), where confidence intervals that are non-overlapping with zero will be considered significant.

Power Analysis for the Mediational Analysis: To assess power to detect mediation, we performed a Monte Carlo-based power analysis using simulated data. We varied the parameter values to roughly correspond to Cohen's criteria for small, medium, and large effects. This resulted in a total of 27 conditions, which we examined at our target sample size of 200. Each

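### Task order is counterbalanced, but the analysis plan mentions no order term and its covariate rule would normally screen one out: a small, outcome-specific loss of precision

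*Combined protocol and SAP*

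**What the plan says.** Section 5.1 states that "150 target children (10- to 15-year-olds) will be randomly assigned to one of three conditions" and that every child does two tasks in the scanner. On their sequence it says: "The order of these two tasks will be counterbalanced". It does not say whether the balancing is done within condition, sex or pubertal group.

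Section 5.2 (Affective Paradigms) numbers the tasks. Emotional face matching is the first and the go/no-go task is the second, with a break between them. The reverse order is not mentioned.

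Section 15.1 screens potential covariates. Those related to both the independent variables (condition, sex, pubertal stage) and the outcome are controlled for. The others, it says, "will not need to be included in the analyses to obtain unbiased estimates". The first-level fMRI model in the same section has a task predictor, head-motion regressors and censoring regressors.

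Section 15.2 describes the power model as "controlling for the 12 covariates, all two-way interactions, and the main effects (the most complex model considered in our primary analysis, see Equation 1 below". The 12 covariates are not listed, and Equation 1 does not appear in the available text. Section 15.3 says the primary analysis begins by "testing the three-way interaction between social buffering condition, sex, and pubertal stage for all outcomes". None of these places mentions task order.

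**The concern.** Order is a factor that the trial itself sets and can record without error. The usual practice is to carry such a factor into the model. The 15.1 rule works against this because it asks only whether omitting a variable would cause bias, and does not consider precision. If counterbalancing succeeds, order is unrelated to condition, sex and pubertal stage. It then fails the first half of the rule however strongly it predicts the outcome.

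Three mechanisms could make order matter:

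- habituation specific to one task;
- carry-over that differs according to which task comes first;
- for the physiological measures, time since baseline. Section 5.2 forms responses by regressing task values on a resting scan taken before both tasks, so the interval from baseline to a given task depends on order.

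Variance from these sources would stay in the error term and widen the standard errors of the condition effects and interactions. A decision about order made only after the data are seen would also be discretionary.

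**Working it through.** **Inputs from the documents.** Three conditions and 150 target children (5.1, 10.1). Power model: "assuming $n = 200$, a $\alpha = .05$, and power = .80 with 12 covariates in our model" (15.2). Stated detectable effects: "we should be able to detect an f^2 of 0.056" at n = 200 and "we will still have an f^2 of .070" at n = 160 (15.2).

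**Assumed input.** The share r of residual variance due to order is not given. I take 0%, 2%, 5% and 10%.

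**Step 1: reproduce the plan's figures.** The test is an F test for an R² increment with noncentrality λ = f²(u + v + 1). With three conditions the three-way interaction has u = 2. Predictors: 12 covariates + 4 main-effect df + 5 two-way df + 2 three-way df = 23, so v = n − 24.

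- n = 200, v = 176: detectable f² = 0.0548 (stated 0.056, at which power is 80.9%).
- n = 160, v = 136: detectable f² = 0.0709 (stated .070, at which power is 79.5%).

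The agreement is close enough to use this model. A four-condition version (u = 3, 27 predictors) gives 0.0634 and 0.0826 and does not fit.

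**Step 2: baseline at the planned analysis size.** At n = 150, v = 126 and the detectable f² is 0.0765 at 80.0% power with no order term.

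**Step 3: add order as one fixed term.** v falls by 1 to 125, and a given effect f² becomes f²/(1 − r). The detectable f² on the original variance scale is the new value times (1 − r). The standard-error ratio, with the term against without, is √[(1 − r) × 126/125]. The gain in equivalent children, before the lost degree of freedom, is 150 × (1/(1 − r) − 1).

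| Assumed r | Equivalent children | Detectable f² (original scale) | Power at f² = 0.0765 | SE ratio |
|---|---|---|---|---|
| no order term | – | 0.0765 | 80.0% | 1 |
| 0% | 0 | 0.0771 | 79.7% | 1.0040 |
| 2% | 3.1 | 0.0756 | 80.5% | 0.9939 |
| 5% | 7.9 | 0.0732 | 81.8% | 0.9786 |
| 10% | 16.7 | 0.0694 | 83.9% | 0.9525 |

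The lost degree of freedom takes back about one child. Break-even on the standard error is at 1 − r = 125/126, that is r = 1/126, or about 0.8%.

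Read the other way, omitting order makes standard errors 1/0.9786 = 1.022 times (r = 5%) or 1/0.9525 = 1.050 times (r = 10%) as large as they would be with the term.

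**Step 4: the same check at the plan's n = 200.** Power at f² = 0.056 moves from 80.9% to 80.7%, 81.5%, 82.8% and 84.9% for r = 0%, 2%, 5% and 10%.

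**The case against.** **The model is not fully visible.** Order could be among the 12 unlisted covariates or in the missing equation. The firm statement is therefore that no order term is mentioned, not that one is known to be absent. The 15.1 rule makes its inclusion unlikely.

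**Much of an order effect may cancel.** Every child does both tasks. If an outcome weights the two tasks equally, a common first-versus-second effect adds the same amount for everyone. Neural outcomes are within-task contrasts of aversive against safe stimuli, and salivary hormones are reduced to one AUCi per analyte from samples across the session. Pure level or position shifts therefore partly cancel. This stands: one range of r cannot be applied to all outcomes. Task-specific habituation, asymmetric carry-over and time since the resting baseline can remain. Section 15.1 also does not say whether each regional value comes from one task or both.

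**A reader might infer that the condition comparisons are biased, or that chance imbalance of order goes uncorrected.** The documents do not support this. With order balanced there is no bias. The 15.1 rule is an empirical screen, so if order is among the variables screened, a detectable imbalance would pass its first half, and order would enter if it also related to the outcome. Only an imbalance too small to detect would escape. Nor can balance within condition be taken as given, since 5.1 does not state it.

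**The sequence may be fixed.** If the numbering in 5.2 is the real running order, order is constant and no term can be fitted. The numbering may be only descriptive, but the two sections need to agree.

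**Conclusion.** The point holds as a modest one about precision. The plan controls task order by design, mentions no order term in the analysis, and has a covariate rule that would normally exclude a balanced order factor.

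At n = 150 the gain from including it is about 2 to 4 power points if order explains 5% to 10% of residual variance. The loss is about 0.3 points if it explains none. These shares are assumptions, and the gain will differ by outcome and may be negligible for some. The calculation also assumes that order is balanced and that the 15.2 model is as reconstructed above.

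The validity of the tests is not in question: at worst they are mildly conservative. Severity is low. The gap between the n = 200 used for power and the 150 children planned for analysis matters more (detectable f² of 0.0548 against 0.0765) and is a separate point.

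**What to change.** 1. In 15.3, prespecify task order (faces first or go/no-go first) as a fixed term in the primary neural, cortisol and physiological models, exempt from the 15.1 covariate screen.
2. In 5.1, state that order is counterbalanced within each condition.
3. Reconcile 5.1 with 5.2, so that 5.2 either describes both sequences or makes clear that its numbering is only descriptive.
4. For each outcome, state whether it comes from one task or both, so that it is clear where order can matter. An order-by-condition sensitivity check could be added.

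The cost is a few lines of text and one degree of freedom per model. No extra data are needed beyond recording each child's task order.
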